7. INTERIM ANALYSES

The study may be unblinded for Sponsor internal decision-making purposes when $\geq 90\%$ of subjects have reached 24 weeks post-randomization (or discontinued prior to the Week 24 visit), and dissemination of these results will be limited to the unblinded reporting team and Sponsor management. The sponsor personnel who are unblinded will be separate from the study team. The sponsor will still maintain the blind for study team members who will be involved in daily study conduct, study management, safety, and data monitoring through the completion of the study. Investigators and subjects will remain blinded. There will be no impact on B7981015 study conduct, analysis, or reporting.

This study will use an external data monitoring committee (E-DMC).

The E-DMC will be responsible for ongoing monitoring of the safety of subjects in the study according to the charter.

9. APPENDICES

9.1. Definition and Use of Visit Windows in Reporting

Visit windows will be used for efficacy and PRO variables, and for any safety data that display or summarize by study visit.

Table 6. Visit Windows

Visit Label	Target Day	Definition
Baseline	1	<=Day 1
Week 2	15	Days 2 to 21
Week 4	29	Days 22 to 42
Week 8	57	Days 43 to 70
Week 12	85	Days 71 to 105
Week 18	127	Days 106 to 147
Week 24	169	Day 148 to 179 and <=EDay ^a 1
Week 26	183	Days 180 to 189 and >EDay 1
Week 28	197	Days 190 to 217 and >EDay 1
Week 34	239	Days 218 to 259 and >EDay 1
Week 40	281	Days 260 to 308 and >EDay 1
Week 48	337	≥Day 309 and >EDay 1

- a. EDay =relative day of the first dose date in the extension phase based on dosing log data after week 24 visit. If Week 24 dose log is missing, earliest dosing date from Week 26 and onward will be considered start of Extension.

The Baseline value is defined in [Section 3.3](#).

Some endpoints were not scheduled to be assessed at each visit. In this case, the unscheduled ‘windowed’ visit will be moved to the next scheduled windowed visit for analysis and reporting. For example, HADS were not to be assessed at Week 18, Week 28, Week 34 and Week 40, if data falls under Week 18 it will be treated as Week 24; and data that falls under Weeks 28, 34, 40 will be treated as Week 48.

If more than one observation falls within a visit window, the observation that is the closest to the targeted day will be used for the summary tables. If two visits are equally distant from the target day, the data from the later visit will be used.

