#### **1.4.2. Phase 2a Study in Rheumatoid Arthritis**

The completed Phase 2a study B7981006 was an 8-week randomized, double-blind, placebo-controlled, parallel-group, multi-center study in subjects with moderate-to-severe active rheumatoid arthritis (RA) with an inadequate response to methotrexate. A total of 70 subjects were randomized to study treatment; 28 subjects received placebo and 42 subjects received PF-06651600 (200 mg QD).

PF-06651600 was determined to be generally safe and well tolerated in this study. There were no deaths or SAEs. TEAEs were numerically higher in subjects receiving PF-06651600 compared to those receiving placebo. The TEAEs reported in more than 5% subjects with RA receiving PF-06651600 were influenza and lymphopenia. The majority of the TEAEs were mild in severity. There was 1 mild case of herpes simplex in the PF-06651600 group that was considered to be treatment-related with no cases in the placebo group. There were no clinically relevant changes in vital signs, electrocardiogram (ECG), or audiometric assessments. By the Week 8 time point (as early as 2 weeks), in the PF-06651600 group, there were decreases in the median platelet counts (25% change from baseline), lymphocyte counts (21% change from baseline), neutrophil counts (24% change from baseline), and hemoglobin (3% change from baseline). None of these were deemed to be clinically relevant by the investigator and values returned to near baseline by the 12-week follow-up visit.

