### **6.3. Follow-up Period**

#### **6.3.1. Visit 14, End of Study/Follow-up**

If a subject discontinues from the study for any reason other than death, lost to follow-up, or withdrawal of consent, a Follow-Up Visit must be performed within 28 (+7 days) after the Early Termination visit. In addition, all subjects who complete the study but do not enter the long-term extension study must have a Follow-Up Visit within 28 (+7 days) of End of Treatment visit.

The following procedures will be completed:

- Obtain vital signs: pulse rate, blood pressure, respiratory rate (after at least 5 minutes of rest), and temperature.
- Conduct targeted physical examination.
- Obtain fasting samples for fasting lipid panel.
- Obtain samples for laboratory testing: hematology, blood chemistry, and urinalysis.
- Confirm whether menarche has started in previously premenarchal subjects. If menarche has started, the subject must undergo a pregnancy test.
- Perform urine pregnancy test (female subjects of childbearing potential only).
- Confirm proper contraception is being used.
- Review any changes in the subject's concomitant treatments information.
- Assess for occurrence of AEs.

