Week 8 (Day 57)	±7 days (Day 50-64)	-7/+14 days (Day 50-71)
Week 12 (Day 85)	±7 days (Day 82-88)	-7/+21 days (Day 82-106)
Week 18 (Day 127)	±7 days (Day 120-134)	-7/+21 days (Day 120-148)
Week 24 (Day 169)	±7 days (Day 162-176)	±7 days (Day 162-176)
Week 26 (Day 183)	±3 days (Day 180-186)	±3 days (Day 180-186)
Week 28 (Day 197)	±3 days (Day 194-200)	-3/+21 days (Day 194-218)
Week 34 (Day 239)	±7 days (Day 232-246)	-7/+21 days (Day 232-260)
Week 40 (Day 281)	±7 days (Day 274-288)	-7/+30 days (Day 274-311)
Week 48 (Day 337) c	±7 days (Day 330-344)	-7/+30 days (Day 330-367)

a. These are the same as the windows in the protocol [Schedule of Activities](#).

b. Laboratory results must be received and reviewed by the investigator within 14 days after they are collected to determine eligibility to continue dosing. In addition, laboratory test results from the previous visit must be available and reviewed by the investigator prior to shipping investigational product at the current visit.

c. If subject is rolling over into B7981032, labs must be collected prior to enrollment in B7981032.

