6.7.3. Vital Signs, including Height and Weight

Vital signs will be summarized at baseline and all post-baseline visits. The data will be listed and summarized in accordance with the Pfizer reporting standards. Summaries of incidence of clinically significant abnormalities will include frequency and percentages.

Height and weight will be summarized at enrollment/baseline, Week 24, and Week 48.

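### SAP Table 6 has no Follow-up row or last-dose limit, so early discontinuers' off-drug Visit 14 laboratory and vital-sign values are reported under later treatment-period weeks

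*SAP*

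**What the plan says.** SAP Section 9.1 sets the scope of the visit windows: "Visit windows will be used for efficacy and PRO variables, and for any safety data that display or summarize by study visit". Table 6 has rows for Baseline and Weeks 2 to 48. The day ranges are contiguous from Day 2, and the last row is "≥Day 309 and >EDay 1", with no upper limit. There is no row for Early Termination or Follow-up. The only dosing-related condition is EDay, attached to the rows from Week 24 on: "EDay =relative day of the first dose date in the extension phase based on dosing log data after week 24 visit". It separates the placebo-controlled phase from the extension and does not refer to the last dose. The rule for competing records in the summary tables opens: "If more than one observation falls within a visit window, the observation that is the closest to the targeted day will be used for the". On a tie in distance, the later visit counts.

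Visit 14 (Protocol Section 6.3.1) falls 28 (+7) days after the ET or end-of-treatment visit, and ET is performed on the last dosing day or as soon as possible after it (Section 6.3.2). Among the Visit 14 procedures are vital signs, fasting lipids and "Obtain samples for laboratory testing: hematology, blood chemistry, and urinalysis". On reporting, SAP Section 6.7.3 says "Vital signs will be summarized at baseline and all post-baseline visits". Sections 6.7.2 and 6.7.3 otherwise defer to sponsor reporting standards that are not part of the documents.

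**The concern.** Visit 14 is off drug by design, yet the windowing rule can only give it a treatment-week label or, for some subjects, no clear label. Blood counts are where this matters. The protocol reports falls in platelets and lymphocytes on drug, and for the rheumatoid arthritis study it says "values returned to near baseline by the 12-week follow-up visit". A recovered value shown in a treatment-week column makes the drug's effect on that week's mean look smaller.

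The subjects concerned are mainly those who stopped early, some of them for a laboratory abnormality under Protocol Appendix 3.2. That appendix also asks for follow-up from one week after the last dose until the event resolves or is stable, and Table 6 has no rule keeping those records out of the treatment weeks either.

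**Working it through.** **Inputs.** Table 6 day ranges, target days and tie rule (SAP 9.1). Follow-up lag of 28 to 35 days (Protocol 6.3.1, 6.3.2). The Schedule of Activities footnote on early discontinuation says 28 (±7), so 21 days serves as a sensitivity case. Week 48 visit on Day 337 ±7 (Protocol 6.2.12). The plan states no figure on this point to reproduce.

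**Step 1: label given to Visit 14.** With last dose and ET on Day L, follow-up is on Day L + 28 to L + 35.

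| Stop day L | Follow-up day | Table 6 row (days) |
|---|---|---|
| 7 | 35 to 42 | Week 4 (22–42) |
| 29 | 57 to 64 | Week 8 (43–70) |
| 57 | 85 to 92 | Week 12 (71–105) |
| 85 | 113 to 120 | Week 18 (106–147) |
| 197 | 225 to 232 | Week 34 (218–259) |
| 239 | 267 to 274 | Week 40 (260–308) |
| 281 | 309 to 316 | Week 48 (309 on) |

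None of these depends on an undefined EDay: the follow-up day is either before Day 148 or after extension dosing began.

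**Step 2: every stop day from 1 to 337.** Assume scheduled visits on target days and ET on the last-dose day, apply the closest-to-target rule, and set EDay aside. The Visit 14 value is then the one reported for:

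| Lag (days) | Hematology | Chemistry and vital signs |
|---|---|---|
| 21 | 269 (80%) | 263 (78%) |
| 28 | 292 (87%) | 286 (85%) |
| 35 | 303 (90%) | 300 (89%) |

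These count possible stop days, not subjects.

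**Step 3: EDay.** A subject who never took an extension dose has no EDay. Follow-up then falls on or after Day 180 for stops on Days 152 to 168 (28-day lag) or 145 to 168 (35-day lag). Removing those 17 or 24 days leaves 275 and 269 (28 days), or 279 and 276 (35 days), for hematology and chemistry/vital signs respectively. If an undefined EDay also fails the Week 24 condition, another 32 days go, leaving 243 and 237, or 247 and 244. The SAP does not say which reading applies.

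**Step 4: both records in the Week 48 row.** For L ≥ 309 at a 28-day lag, the ET record is 337 − L days from target and the follow-up record L + 28 − 337 = L − 309 days. Follow-up is chosen when L − 309 ≤ 337 − L, that is L ≤ 323 (at 323 both are 14 days away and the later one is used). At a 35-day lag, L − 302 ≤ 337 − L gives L ≤ 319. Example: for a stop on Day 315, ET is 22 days from target and follow-up 6, so Week 48 shows the off-drug value.

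**Step 5: completers.** A Week 48 visit on Days 330 to 344 is at most 7 days from target. Follow-up on Days 358 to 379 is 21 to 42 days away. The Week 48 value always wins, so Visit 14 enters only if that value is missing. Subjects who roll over immediately into the long-term study need no Visit 14.

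**Step 6: size.** If a share s of an arm's records at a visit are follow-up records fully back at baseline, the displayed change is the true change × (1 − s). For s = 2%, 5% and 10%, a change of −18% displays as −17.6%, −17.1% and −16.2%, and −24% as −23.5%, −22.8% and −21.6%. The shares are assumptions. The −18% (platelets) and −24% (lymphocytes) are Phase 2a figures from 200 mg induction (Protocol 1.4.1) and are used only for orientation. Each early terminator has one scheduled Visit 14, in one window. An assumed 20% dropout spread evenly over nine windows gives 20/9 = 2.2% of randomized subjects per visit, or 2.2/0.8 = 2.8% if 80% remain, so shares of about 2 to 3% are more plausible than 10%.

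**The case against.** The strongest reply is that laboratory and vital-sign reporting follows sponsor standards, which may already separate follow-up from treatment visits. That cannot be excluded. But Section 9.1 is the study-specific rule, it names by-visit safety data, and nothing in it yields to those standards. If they do handle Visit 14, one line in Table 6 would say so.

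The second reply is that the safety endpoint is the incidence of clinically significant abnormalities, not a by-visit mean. This largely stands. A recovered later value does not erase an earlier abnormal one from a subject-level count, and the discontinuation criteria in SAP Table 7 carry no visit window. Nor is a displaced ET value lost: the selection rule concerns summary tables, and laboratory data are also listed.

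The third reply is that the hematology figures come from 200 mg dosing. This also stands. Counts improved on 50 mg maintenance in Phase 2a, and Protocol Table 2 gives 200 mg only in the first four weeks (sequences A and B) and in Weeks 24 to 28 (sequence F). The documents give no maintenance-phase effect to attenuate.

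A reader might also infer that Week 48 laboratory samples drawn as late as Day 367 under Protocol Appendix 6.3, Table 8, are mislabelled. The documents do not support that. They are scheduled Week 48 samples collected late under public-emergency provisions, and the Week 48 label follows the protocol's own visit identity.

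**Conclusion.** The point holds for two groups: subjects who discontinue early, and completers with no Week 48 value. For them the rule as written reports off-drug Visit 14 laboratory and vital-sign values under treatment-period labels from Week 4 to Week 48. For stops on Days 309 to 323 (28-day lag) or 309 to 319 (35-day lag) it prefers the off-drug value to the on-drug ET value. For subjects with no extension dose, assignment from Day 148 on is unclear.

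A reader might infer that Visit 14 values in general contaminate the treatment columns, or that the safety profile is materially masked. Neither follows. Completers with an in-window Week 48 value and immediate rollovers are unaffected. Table 6 never calls its rows on-treatment, although each post-baseline label is a treatment-period visit.

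The expected effect is a modest pull of by-visit means toward baseline. Its size depends on the dropout rate, the timing of stops, the effect at maintenance doses and the completeness of recovery, none of which the documents fix. Efficacy and PRO results are unaffected because neither is collected at Visit 14. Subject-level incidence is essentially unaffected, provided it counts all post-baseline records and not only window-selected ones.

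**What to change.** In SAP Section 9.1:

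- Add a Follow-up row to Table 6 for Visit 14.
- State that records after the ET or end-of-treatment visit, or beyond a number of days after last dose that the sponsor sets, go to that row and cannot displace an on-treatment record. Scheduled Week 48 samples drawn late under Protocol Appendix 6.3 keep their Week 48 label.
- State how EDay is handled for subjects who never took an extension dose.

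With a Follow-up row, or a cut-off shorter than the follow-up lag, none of the 337 stop days would place a Visit 14 value in a Week 2 to Week 48 column. The Visit 14 timing, 28 (+7) days in Protocol 6.3.1 and 6.3.2 but 28 (±7) in the Schedule of Activities footnote, should be reconciled at the same time.

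The cost is SAP wording, one programming condition on the last-dose or ET date, and slightly fewer records in the later by-visit columns. No new data are needed.

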## Appendix 6.3. Alternative Facilities for Safety Assessments

### Laboratory Testing

With the exceptions noted in [Appendix 6.1](#) for Screening and Day 1, if a study subject is unable to visit the site for protocol-specified safety laboratory evaluations, testing may be conducted at a local laboratory if permitted by local regulations. The local laboratory may be a standalone institution or within a hospital. Collection of blood and urine samples may also be performed at the subject's home per [Appendix 6.5](#). The following safety laboratory evaluations may be performed at a local laboratory or in the subject's home:

Hematology;

Serum chemistry;

Fasting lipid panel;

Urinalysis;

Pregnancy testing (for WOCBP);

Refer to the [Schedule of Activities](#) for visits at which these tests are required and to [Section 7.5.7](#) for additional details regarding these tests.

If it is not possible for the subject to have the above tests completed within the visit window specified in the [Schedule of Activities](#), an extended window may be allowed to collect samples for these laboratory tests, provided that the investigator has performed the remote visit as described above, assessed each case, and determined that it would not increase risk to a subject. The extended windows for laboratory sample collection for each study visit are noted in [Table 8](#). These windows apply only to laboratory samples collected during interruptions due to public emergencies, including the COVID-19 pandemic, based upon written notification from Pfizer. If the laboratory samples are not collected within the specified extended window for the visit, the subject must temporarily withhold investigational product until the required laboratory samples can be collected.

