## Appendix 6.4. Investigational Product

If the safety of a trial subject is at risk because they cannot complete required evaluations or adhere to critical mitigation steps, then discontinuing that subject from investigational product must be considered.

Investigational product may be shipped by courier to study subjects if permitted by local regulations and in accordance with storage and transportation requirements for the investigational product. Pfizer does not permit the shipment of investigational product by mail. The tracking record of shipments and the chain of custody of investigational product must be kept in the subject's source documents/medical records.

If a third-party courier engaged by Pfizer or Pfizer's contract research organization (CRO) **is used** for shipping the investigational product, written consent must be documented in the informed consent document prior to shipping investigational product. If a third-party courier engaged by Pfizer or Pfizer's CRO **is not used** for shipping the investigational product, consent must be verbally obtained (or per local guidelines/regulations) and documented in site's source documents prior to shipping investigational product.

Prior to shipping investigational product to a subject, 1) consent must be obtained and documented as described above, 2) all required safety information listed in [Appendix 6.2](#) must have been collected and reviewed by the investigator, 3) the required laboratory tests from the previous visit must have been reviewed by the investigator, and 4) any additional evaluation (if requested based on investigator judgment) must have been performed, with results submitted to and reviewed by the investigator.

Investigational product cannot be shipped to the subject and must be temporarily discontinued if 1) the laboratory tests from the previous visit have not been reviewed by the investigator OR 2) after reviewing the required information (including that from a remote visit), the investigator cannot make an assessment of whether it is safe for the subject to continue investigational product. Refer to [Section 5.5](#) regarding temporary withholding of investigational product.

The study site may deliver the investigational product to subjects using an acceptable delivery method only if this is consistent with local laws and regulations and the site is able to ship the investigational product according to the guidelines provided by the Sponsor in a separate document.

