The amount of investigational product to be shipped should correspond to the amount dispensed per the Impala Quick Reference Guide at the specific study visit which is being conducted remotely. Dispensing and/or shipment of additional investigational product to extend the visit window is not permitted.

Subjects should continue taking the current supply of investigational product until the new supply is received (unless temporary withholding of investigational product is required).

Dosing logs should be shipped with the investigational product.

Study sites should follow up with the subject once the investigational product is received by the subject to review when to start using the new blister cards, the dosing instructions, and completion of the dosing logs.

Subjects should be instructed not to re-use or dispose of any blister cards dispensed at a previous visit.

All blister cards and dosing logs must be returned to the study site at the next on-site visit.

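### SAP Table 6 gives no visit label to a SALT or PGI-C assessment on Day 180 or later but on or before the first extension dose, so an observed Week 24 result can be lost; the effect is probably small

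*SAP*

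**What the plan says.** SAP 9.1 applies the Table 6 windows to all efficacy and PRO variables. The Week 24 row reads "Day 148 to 179 and <=EDay" 1. The Week 26 row reads "Days 180 to 189 and >EDay 1", and the rows for Weeks 28, 34, 40 and 48 carry the same condition of being after EDay 1. Footnote a defines EDay as the "relative day of the first dose date in the extension phase based on dosing log data after week 24 visit". Its one fallback is: "If Week 24 dose log is missing, earliest dosing date from Week 26 and onward will be considered start of Extension".

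The protocol's Week 24 visit window is Day 169 plus or minus 7 days. In Protocol Appendix 6.3, Table 8, the laboratory window for Week 24 is not widened, unlike most other visits; it stays at "7 days (Day 162-176"). If samples are not taken in the window, "the subject must temporarily withhold investigational product until the required laboratory samples can be collected". Appendix 6 requires procedures missed through COVID-19 to be done at the next opportunity, even outside the visit window. Appendix 6.7 restricts SALT and all PROs to on-site visits. Doses on visit days are taken in the clinic (Schedule of Activities, footnote w; Protocol 6.2.7).

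**The concern.** The Week 24 row closes at Day 179, and no later row opens until the subject has taken an extension dose. Whatever lies between has no label. The protocol tells sites to obtain a late SALT in this situation, and the SAP then gives that SALT nowhere to go.

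Week 24 SALT is the primary endpoint in every region (≤20 for the overall study and FDA/PMDA, ≤10 for EMA). Week 24 PGI-C is the EMA key secondary endpoint. A result seen before any extension dose would be replaced by a missing-data rule. None of the planned supplementary analyses restores it: Analyses 2, 2a, 3 and 4a change how a missing value is handled, and none uses the observed value.

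**Working it through.** **1. Table 6 applied as written.**

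| Assessment day | EDay 1 | Label |
|---|---|---|
| 169 | 169 | Week 24 |
| 179 | 179 | Week 24 |
| 180 | 180 | none |
| 185 | 186 | none |
| 190 | 190 | none |
| 185 | 170 | Week 26 |

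With EDay 1 = 180, 185, 189 or 195, the unlabelled pre-extension days are 180, 180-185, 180-189 and 180-195. With EDay 1 at Day 179 or earlier, every day from 180 on has a label. The other rules in SAP 9.1 do not help: moving data to the next scheduled window, and choosing the observation closest to target, both act on data already in a window.

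**2. Can it happen?** The gap starts 180 − 176 = 4 days after the protocol window closes and 180 − 169 = 11 days after target. Suppose no Week 24 samples are taken by Day 176. Drug is withheld, and the subject attends on site on Day 180 or later for samples, SALT and the first extension dose. EDay 1 is then that same day, and no row applies.

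**3. Time off drug at such a visit.** If drug is withheld from Day 177, a SALT on Day d follows d − 177 days off drug: 3 days at Day 180, 10 at Day 187, 12 at Day 189. If supply ended on Day 168 (assumption), it follows d − 169 days: 11 at Day 180 and 20 at Day 189. Two thresholds are relevant. More than 10 days between visits goes to the sponsor for possible withdrawal (Protocol 5.3, 5.5, Appendix 3.2). Six weeks (42 days) or more is a listed deviation for the per-protocol set (SAP 4.2).

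**4. What happens to the record.** The SAP does not say. SAP 5.3.1 applies one rule to missed visits and early discontinuation, and SAP 9.6 codes a visit with insufficient information as missing, so treatment as missing is an inference. For COVID-19 reasons the subject would be excluded in Analysis 1 or imputed under MAR in Analysis 4. For other reasons the subject would count as a non-responder in both.

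**5. Size.** Inputs (Protocol 9.1, SAP 2.2.1): 120 per group, with placebo also 120 after pooling F and G; 29% vs 5% at α = 0.00125 for SALT ≤20; 25% vs 5% at α = 0.01 for SALT ≤10. With p̄ the mean of the two rates:

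power = Φ{[pT − pC − z√(2p̄(1−p̄)/n)] / √([pT(1−pT) + pC(1−pC)]/n)}

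- SALT ≤20: (0.240 − 3.227 × 0.04849)/0.04595 = 1.817, power 96.5%.
- SALT ≤10: (0.200 − 2.576 × 0.04610)/0.04425 = 1.836, power 96.7%.

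Both reproduce the plan's claim of more than 90%. The loss rate f is an assumption of 2-5%, or 2.4-6 of 120 per group. Scoring as non-response multiplies a rate by (1 − f); exclusion lowers n to 118 or 114.

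| Handling of lost results | f | SALT ≤20: difference (points), power | SALT ≤10: difference (points), power |
|---|---|---|---|
| None lost | 0 | 24.0, 96.5% | 20.0, 96.7% |
| Non-response, both arms | 2% | 23.5, 96.0% | 19.6, 96.3% |
| Non-response, both arms | 5% | 22.8, 95.1% | 19.0, 95.5% |
| Non-response, active arm only | 2% | 23.4, 95.8% | 19.5, 96.0% |
| Non-response, active arm only | 5% | 22.6, 94.3% | 18.8, 94.8% |
| Excluded, both arms | 2% | 24.0, 96.2% | 20.0, 96.4% |
| Excluded, both arms | 5% | 24.0, 95.4% | 20.0, 95.7% |

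Exact enumeration of the Miettinen-Nurminen test gives a similar picture for SALT ≤20: 97.9% falls to 96.9% (both arms) or 96.2% (active only) at 5% loss. For PGI-C (55% vs 20%, α = 0.01), power is 99.9% and still 99.7% with 5% lost in the active arm only. If non-response scoring fell on placebo alone, the SALT difference would rise by 0.05 × 5 = 0.25 point.

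**The case against.** Every window must end somewhere, and Day 179 is already 3 days past the protocol window. A later cap also leaves some records out, and Day 189 has no special standing beyond being the end of the Week 26 row. This stands: the cap is a matter of judgement. But the present table does not state a cap and its consequence. It leaves a gap between rows and is silent on the status of what falls there.

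The route to the gap is narrow. "Investigational product may be shipped by courier to study subjects if permitted by local regulations", and a subject who has a remote Week 24 visit and starts couriered extension supply before the on-site SALT is after EDay 1 and does get a later label. The 10-day interruption threshold narrows it further toward the later days. Both points limit frequency, but neither closes the gap: shipment is optional, and "Dispensing and/or shipment of additional investigational product to extend the visit window is not permitted".

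Three stronger readings are tempting, and the documents do not support them.

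- A reader might infer that Day 148-179 results are also lost in subjects who never take an extension dose, for example at an Early Termination visit. EDay is undefined there, and the label depends on how code treats a missing EDay: unlabelled if the comparison is false or missing sorts lowest, Week 24 if missing sorts highest. The condition keeps out data recorded after sequences F and G move to active drug (SAP 2.2), and such a subject has none, so an analyst would sensibly assign Week 24. This is missing detail, not a demonstrated loss.
- A reader might count records by Day 179 but after EDay 1 as wrongly lost. They have no row, but keeping them out of Week 24 is right, because placebo subjects are then on active drug.
- A reader might infer that the primary conclusion is at risk, or that PGI-C is a primary endpoint. The power figures do not support the first, and PGI-C is key secondary for EMA only and secondary elsewhere.

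**Conclusion.** The gap is definite in the text: a pre-extension assessment on Day 180 or later has no visit label, and the protocol's own catch-up and withholding rules can produce one. That such a record is then treated as missing is inferred, not stated.

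The consequence is probably small. No frequency is documented, and the 2-5% range is an assumption. Within it, power for the SALT endpoints stays at 94.3% or above. Exclusion or imputation is roughly neutral on the difference and costs precision; non-response scoring pulls the difference toward zero when both arms or only the active arm are affected. These figures cover the planning assumptions for 200 mg/50 mg at the full regional α, not the other regimens or the split α levels. The change should be made because it is cheap and concerns how a primary-endpoint value is assigned; it is not a threat to the trial's conclusion.

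**What to change.** Amend Table 6 and its derivation code before unblinding, including the possible unblinding once 90% or more of subjects have reached Week 24 (SAP 7):

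- **Documented first extension dose:** define Week 24 as Day 148 through EDay 1, at day level with same-day assessments included as now, and one prespecified upper cap (Day 189, for example). State the status of any pre-extension record after the cap.
- **EDay taken from the Week 26-onward fallback:** keep the Day 179 limit, since the true first extension dose may have been earlier.
- **Clarification:** a subject confirmed to have taken no extension dose meets the condition of being on or before EDay 1, with the window kept at Day 148-179. This does not apply where extension dosing logs are merely missing.
- **Records after EDay 1:** keep them out of Week 24.
- **Sensitivity and reporting:** repeat the primary analyses (Analyses 1 and 4) with the Day 179 limit. List affected records by arm, reason and days off drug, against both the 10-day threshold and the 6-week per-protocol rule.

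The cost is SAP wording, code and one repeat of each primary analysis; no new data are needed. The downside is that a few later assessments, some after a dosing interruption, enter Week 24. The Day 179 repeat shows whether that matters.
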